7.8.1. Primary and sensitivity analyses

The primary efficacy endpoints will be analyzed using the Full Analysis Set with confirmed fibrosis stage F2 or F3 and NAS ≥ 4 at baseline per independent review by a 3-pathologist panel. To evaluate the effect of BIO89-100 on liver histology, the proportions of subjects who met different histological responder criteria (defined in Section 4.1.1 and 4.1.2) at Week 24 will be summarized by treatment group based on central manual reads per central lab biopsy manual.

The Cochran-Mantel-Haenszel (CMH) test stratified by T2DM status (yes vs. no) and fibrosis stage (F2 vs. F3) will be used to compare the proportions of responders at Week 24 in each pegozafermin group versus placebo. The point estimates and 95% CI for the differences in proportions will be calculated. If two or more strata contain small cell counts (<5) that renders the stratified CMH test inappropriate, the primary analysis will use a logistic regression with treatment group indicator, stratification factors and baseline NAS score in the model.

The null hypotheses that there is no significant difference in proportion of subjects who met histological responder definition will be tested at significance level of 0.05 (two-sided) for each pegozafermin treatment group versus placebo. Type-1 error will not be adjusted for the multiplicity. Supportive analyses of each treatment QW arm vs. placebo QW arm and 44 mg Q2W arm vs. placebo Q2W arm will also be performed. The primary analysis will be repeated in all subjects with baseline and follow-up biopsies as a supportive analysis.

NAS grade of each component and NASH CRN fibrosis stage, along the shifts from baseline, will be summarized at Week 24 and different read source (central manual reads or PathAI machine reads). NAS total score and fibrosis score will be summarized descriptively at each protocol scheduled visit and different read source.

In addition to the primary analysis, standard sensitivity analyses, namely, sensitivity analyses based on the hypothetical (missingness at random) strategy, return-to-baseline imputation and control-based imputation, will be conducted. The details of these analyses are presented in Table 5. In all cases, a multiple imputation approach will be applied and imputation models will be based on a Bayesian logistic regression model with subject baseline fibrosis stage, diabetes status, age, gender and baseline NAS score included in the model. The estimated effects and associated standard errors from the individual completed data sets will be combined using Rubin's rules to produce a single inferential statement (treatment effect, standard error and p-value).

Table 5: Primary and sensitivity analyses for three types of ICEs

Analysis	ICE-1	ICE-2	ICE-3
Primary analysis	Use all collected outcomes regardless of ICEs. Impute missing outcomes based on an imputation model informed by the relevant baseline data and type of ICE (“none”,1,2,3). If most subjects with ICE have missing outcomes, type of ICE covariate will be removed from the imputation model.		
Sensitivity analysis by ICE type	Set all post-baseline outcomes as missing. Impute missing outcomes based on an imputation model informed by the baseline data alone (return-to-baseline).	Set all outcomes following ICE as missing. Impute missing outcomes based on an imputation model informed by patients who did not have any of the three ICEs using only the data from the placebo arm.	Set all outcomes following ICE as missing. Impute missing outcomes based on an imputation model informed by patients who did not have any of the three ICEs using only the data from the treatment arms.

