Although the ICEs' defined above will be all handled by the same treatment policy strategy for the primary estimand, various sensitivity analyses (SA) will be conducted that will incorporate different strategies, depending on the type of ICE. For the purposes of sensitivity analysis, patients who experienced any of the listed ICEs (ICE-1,2,3), the outcomes for the primary efficacy endpoint will be considered missing starting from the occurrence of each ICE (even if outcomes are collected following an ICE) and then the missing outcomes will be imputed using appropriate imputation strategies.

For ICE-1, the SA will use the "return to baseline" hypothetical strategy, implying no benefits have been received for such patients from randomization until the end of the treatment period. The missing outcomes will be imputed using a relevant regression model fitted to the baseline data within each treatment arm with relevant patient baseline covariates and stratification factors included as covariates.

For ICE-2, SA will be handled with the "control-based" hypothetical strategy implying that patients would have switched to the control treatment (i.e., placebo) starting from the occurrence of ICE-2 to the end of the treatment period. The missing outcomes will be imputed from a similar regression model fitted to the placebo arm alone with relevant patient baseline covariates and stratification factors as covariates.

For ICE-3, SA will be handled using a hypothetical strategy that assumes that patients would have continued their assigned treatment starting from ICE3. The missing outcomes will be imputed using the same model as for ICE-2 but fitted to each respective treatment arm.

Missing data due to reasons unrelated to the intercurrent events (ICE-1, 2, 3), e.g., missingness caused by study termination by sponsor, will be imputed using the same model as for ICE-3.

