For ICE-3, SA will be handled using a hypothetical strategy that assumes that patients would have continued their assigned treatment starting from ICE-3. The missing outcomes will be imputed using the same model as for ICE-2 but fitted to each respective treatment arm.

Missing data due to reasons unrelated to the intercurrent events (ICE-1, 2, 3), e.g., missingness caused by study termination by sponsor, will be imputed using the same model as for ICE-3.

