7.8.1.2. Sensitivity analysis

7.8.1.2.1. Per ICE type

Return-to-baseline imputation will be applied as described in Table 5 for patients who experienced ICE-1. For patients with ICE-1, set both week 24 outcomes to missing and impute the data using the baseline data alone.

Control-based imputation will be applied as described in Table 5 for patients who experienced ICE-2. Set all outcomes following ICE to missing in the treatment arm. For the placebo arm, keep only patients with no ICEs.

Treatment-continuation imputation will be applied as described in Table 5 for patients who experienced ICE-3. Set both outcomes following ICE to missing and impute the data by patients who did not have any of the three ICEs in the respective randomized arm.

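### SAP Table 5 does not confine ICE-3 imputation to the subject's own randomised arm, contrary to the SAP text and the protocol; a pooled donor set would shrink the difference in the per-ICE sensitivity analysis

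*SAP*

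**What the plan says.** SAP 7.8.1 points to Table 5 for the details of the sensitivity analyses. In the row for the analysis by ICE type, the ICE-3 cell sets post-event outcomes to missing and imputes them from a model informed by patients "who did not have any of the three ICEs using only the data from the treatment arms". The neighbouring ICE-2 cell is built the same way but ends by naming the placebo arm.

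Three other places define the ICE-3 donors differently:

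- SAP 7.8: the missing outcomes "will be imputed using the same model as for ICE-2 but fitted to each respective treatment arm".
- SAP 7.8.1.2.1: set the outcomes to missing and "impute the data by patients who did not have any of the three ICEs in the respective randomized arm". The same paragraph says that the method is applied as Table 5 describes.
- Protocol 9.1.1: "The missing outcomes will be imputed using the same model as for ICE-2 but fitted to each respective treatment arm".

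SAP 7.8 also gives the assumption behind the method, a hypothetical strategy that "assumes that patients would have continued their assigned treatment starting from ICE-3".

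For ICE-2, SAP 7.8.1.2.1 mentions setting outcomes to missing only for the treatment arm and then says: "For the placebo arm, keep only patients with no ICEs". It does not say whether this describes the imputation model or the analysed data.

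**The concern.** The ICE-3 strategy is a continuation assumption. For a placebo subject, the assigned treatment is placebo, so the donors must be placebo subjects. For a 15 mg subject they must be 15 mg subjects. Table 5 does not say this, and its wording can be taken to mean one donor set shared across arms.

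The text cannot simply be assumed to override the table, because SAP 7.8.1 and 7.8.1.2.1 both refer to it. Protocol section 9 gives the SAP precedence over the protocol, so the protocol's agreement with the SAP text does not settle the matter either.

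At stake is what this sensitivity analysis can tell the reader. It is meant to test one stated assumption about subjects with other events. With a shared donor set it would test a different one, and a gap from the primary result could not be interpreted.

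**Working it through.** **Inputs from SAP 3.5.** Placebo response is 15% (NASH resolution) and 20% (fibrosis improvement). Pegozafermin response is 45% and 50%. There are 64 subjects on pooled placebo (42 + 22), 16 on 15 mg, 64 on 30 mg and 40 on 44 mg. The test is two-sided at 0.05, with dropout up to 15%.

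**The plan's own figures.** The SAP gives no figure for the ICE sensitivity analysis, so the only check is that the stated powers follow from these rates. A two-proportion test with pooled variance and each n multiplied by 0.85 gives:

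| Comparison | n analysed | Computed | Stated |
|---|---|---|---|
| 30 mg vs placebo | 54.4 vs 54.4 | 93.8% / 91.8% | 94% / 92% |
| 44 mg vs placebo | 34.0 vs 54.4 | 87.1% / 84.0% | 87% / 83% |

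All four agree within about one point, so these are the right planning rates.

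**Formula.** Let f be the share of an arm imputed with the ICE-3 model, p the arm's own rate and d the donor rate. The completed rate is (1 − f) × p + f × d. With the same f in both arms, the expected difference is (1 − f)(p₁ − p₀) + f(d₁ − d₀).

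- Own-arm donors: d₁ = p₁ and d₀ = p₀, so the difference stays at 30.0 points.
- One common donor set: d₁ = d₀, so the difference is (1 − f) × 30.

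The documents do not give f. I assume 5, 10 and 15%:

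| f | Placebo, NASH resolution (donors at 45%) | Placebo, fibrosis improvement (donors at 50%) | Difference, either endpoint |
|---|---|---|---|
| 5% | 0.95 × 15 + 0.05 × 45 = 16.5% | 0.95 × 20 + 0.05 × 50 = 21.5% | 0.95 × 30 = 28.5 |
| 10% | 0.90 × 15 + 0.10 × 45 = 18.0% | 0.90 × 20 + 0.10 × 50 = 23.0% | 0.90 × 30 = 27.0 |
| 15% | 0.85 × 15 + 0.15 × 45 = 19.5% | 0.85 × 20 + 0.15 × 50 = 24.5% | 0.85 × 30 = 25.5 |

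**Does it matter which arms are pooled?** Suppose the donors come from all arms, with every dose at 45%. The donor rate is (64 × 15 + 120 × 45)/184 = 34.6%. At f = 10%, placebo becomes 13.5 + 3.46 = 16.96% and active becomes 40.5 + 3.46 = 43.96%. The difference is again 27.0. Any shared donor set gives the same shrinkage, provided that covariates are similar across arms. SAP 7.8.1 lists fibrosis stage, diabetes status, age, gender and baseline NAS for these models, so no listed term would restore the arm difference.

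**If the doses differ.** Assume 25% at 15 mg, 35% at 44 mg and 45% at 30 mg. The active donor rate is (16 × 25 + 40 × 35 + 64 × 45)/120 = 39%. At f = 15%, 30 mg becomes 38.25 + 5.85 = 44.1% and placebo becomes 12.75 + 5.85 = 18.6%, a difference of 25.5. The 15 mg arm becomes 21.25 + 5.85 = 27.1%, so its difference is 8.5 instead of 10.

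**Rough power.** At 64 vs 64, treating completed data as observed, power falls from 96.8% to 94.7 / 91.7 / 87.9% for NASH resolution. For fibrosis improvement it falls from 95.4% to 92.9 / 89.7 / 85.6%. These figures ignore the between-imputation variance and are only indicative.

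**The case against.** The strongest reply is that the intent is plain. Two SAP sections and the protocol say own arm, 7.8.1.2.1 is where the method is applied, and giving a placebo subject active-arm outcomes would contradict the stated continuation assumption. A careful programmer would probably get it right. That makes the point small, but it does not remove it: the cell is wrong or incomplete as written, and the text refers to it.

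Several stronger readings are tempting, and the documents do not support them.

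- *The cell means active arms only.* The contrast with the ICE-2 cell suggests this, and 7.8.1.2.1 sets treatment arm against placebo arm. But usage is mixed: Protocol 4.2 calls placebo QW a treatment arm, and SAP 7.8 fits the ICE-1 model within each treatment arm, apparently including placebo. The active-only reading is possible but not established. The shrinkage does not depend on it.
- *The rule governs most missing outcomes.* ICE-3 is the catch-all category, but no ICE counts are given. SAP 7.8 sends missing data unrelated to any ICE to the ICE-3 model directly after defining that model by respective arm, so those data follow the own-arm rule.
- *Placebo subjects with an ICE are dropped under ICE-2.* In Table 5, event-free placebo patients are the group informing the model. SAP 7.8 sets outcomes after any ICE to missing and imputes them, and the analysis is in the Full Analysis Set. The sentence most naturally describes the donor set. What remains is that 7.8.1.2.1 does not spell out the handling of placebo subjects with ICE-2.
- *The trial's conclusion is biased in favour of the drug.* With equal imputed shares, the ICE-3 effect is toward no difference, and it is confined to one sensitivity analysis. SAP 7.8.1.1 imputes the primary analysis by trial arm, or with treatment as a covariate if data are sparse. The other sensitivity analyses in 7.8.1.2 do not use this per-ICE rule.

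**Conclusion.** The inconsistency stands as a minor point. The ICE-3 cell of Table 5 conflicts with SAP 7.8, SAP 7.8.1.2.1, Protocol 9.1.1 and the continuation assumption. If it is programmed with any pooled donor set, the per-ICE sensitivity analysis is attenuated by the fraction imputed: 1.5, 3.0 or 4.5 points off a planned 30 at shares of 5, 10 or 15%.

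This rests on the planning rates, on similar covariates across arms, and on the same imputed share in each arm. The shares are my assumption; the only related figure in the plan is overall dropout of up to 15%, which is not an ICE-3 rate. With unequal shares f₁ (active) and f₀ (placebo), the difference becomes (p₁ − p₀) − f₁(p₁ − d) − f₀(d − p₀). This is still a reduction whenever d lies between the two arms' rates. For a low dose responding below the pooled donor rate, the direction would depend on the two shares.

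The ICE-2 sentence needs clarifying, but there is no basis for saying that it removes placebo subjects.

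**What to change.** 1. **Table 5, ICE-3 cell.** Replace the closing words with a statement that the model is informed by patients free of all three ICEs in the subject's own randomised arm, placebo included. This agrees with SAP 7.8, SAP 7.8.1.2.1 and Protocol 9.1.1.

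2. **SAP 7.8.1.2.1, ICE-2 paragraph.** State that restricting placebo to event-free patients defines the donor set for the imputation model. Add that placebo subjects with ICE-2 stay in the analysis, with post-event outcomes set to missing and imputed from that model. Limit this to ICE-2: placebo subjects with ICE-1 or ICE-3 follow their own rules. A broader sentence would override return-to-baseline for placebo subjects with ICE-1.

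The cost is two sentences in the SAP, with no change to the design, the data collected or the primary analysis. They should be settled before the database is unblinded for the primary analysis, which is when Protocol 9.4 requires the SAP to be final.

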7.8.1.1. Primary analysis

The primary analysis will be carried out using an MI-based strategy that includes the following three steps:

- Step 1. Missing outcomes will be imputed a large number of times ($M=100$) using PROC MI based on the model outlined in Table 5 based on a logistic regression model.
- Step 2. The Cochran-Mantel-Haenszel (CMH) test stratified by T2DM status (yes vs. no) and fibrosis stage (F2 vs. F3) will be applied to each completed data set to compare the proportions of responders at Week 24 between each pegozafermin group and placebo, adjusting for the stratification factors. The point estimates and associated standard errors for the differences in proportions as well as CMH test statistics will be calculated.
- Step 3. The CMH summaries from individual completed sets will be combined using Rubin’s rules to produce a single inferential statement (treatment effect, standard error, 95% confidence interval and p-value) via PROC MIANALYZE.

Note that a patient can have only one ICE (classified as ICE-1, -2, -3) or none (0). Once an ICE of specific type has occurred, the status of ICE variables remains fixed at that value until the end of the trial. All collected data are used in imputation. Imputation is done by the trial arm (TRT) but, if the data are sparse, instead of imputing by TRT, include TRT as covariate.

7.8.1.2. Sensitivity analysis

7.8.1.2.1. Per ICE type

Return-to-baseline imputation will be applied as described in Table 5 for patients who experienced ICE-1. For patients with ICE-1, set both week 24 outcomes to missing and impute the data using the baseline data alone.

Control-based imputation will be applied as described in Table 5 for patients who experienced ICE-2. Set all outcomes following ICE to missing in the treatment arm. For the placebo arm, keep only patients with no ICEs.

Treatment-continuation imputation will be applied as described in Table 5 for patients who experienced ICE-3. Set both outcomes following ICE to missing and impute the data by patients who did not have any of the three ICEs in the respective randomized arm.

7.8.1.2.2. Randomization period as an additional stratification factor

Sensitivity analysis using randomization time period (randomized before/after protocol amendment 2) as an additional stratification factor will be performed.

7.8.1.2.3. Inclusion of subjects randomized but deemed ineligible per the 3-panel

The primary analysis will be repeated by including subjects randomized and received at least 1 dose of IP but deemed ineligible per the 3-panel consensus read i.e., subjects with fibrosis stage F1 or F4 or NAS < 4 at baseline per the 3-panel consensus read.

